3.7.3 Patient global impression of severity and patient global impression of change

The PGI-S is a single item designed to capture the patient's perception of overall symptom severity at the time of completion using a 6-point categorical response scale: 0 – no symptoms; 1 – very mild; 2 – mild; 3 – moderate; 4 – severe; 5 – very severe.

The PGI-C captures the patient's overall evaluation of response to treatment. The patients are asked to report the degree to which they have changed since entering the treatment period using a 7-point scale: 1 – much better; 2 – moderately better; 3 – a little better; 4 – about the same; 5 – a little worse; 6 – moderately worse; and 7 – much worse.

Patients will be categorized according to the following PGI-C responses post-baseline:

- About the same, a little worse, moderately worse, much worse \rightarrow Not better
- Much better, moderately better, a little better \rightarrow At least a little better
- Much better, moderately better \rightarrow At least moderately better
- Much better \rightarrow Much better

3.7.4 Healthcare resource utilisation (HRU)

The following unplanned/unscheduled healthcare resource use (HRU) due to (a) nasal polyps, (b) asthma exacerbation, and (c) other reasons will be collected.

- General and intensive care hospitalisations and lengths of stay
- Emergency room visits
- Urgent care visits

For each category above, the crude rates of HRU during the DB period (as defined in Section 3.1.1) will be calculated, where the *crude rate* = (total days of HRU use/total days during double-blind period).

3.8 Safety outcome variables

According to the SoA Table 2 and Table 3 in the CSP, safety assessments (including AE, haematology, clinical chemistry, vital signs, etc.) will be collected during the DB period and the OLE period, except that ECG is collected only during the DB period.

No safety data will be imputed. The handling of partial/missing dates for AEs and prior/concomitant medications is detailed in Appendix 8.6.1. Duration of AEs and prior/concomitant medications will not be calculated using imputed dates and will instead be set to missing.

3.8.1 Adverse events

Adverse events experienced by patients will be collected throughout the entire study and will be coded by the AstraZeneca designee using the latest version of the Medical Dictionary for Regulatory Activities (MedDRA).

AEs will be separated according to their onset date into the following study periods:

- AEs occurring during the DB period: date of first dose of IP in DB period \leq AE onset date \leq EoDB, except any AE that starts on or after the date of first OLE dose should only be counted in the OLE and not in the DB period.
- AEs occurring during the OLE period: date of first dose of IP in OLE \leq AE onset date \leq study completion or withdrawal date
- AE occurring during the extended follow-up (applicable to CSP v1.0 or v2.0):
 - for patients who did not enter the OLE: EoDB $<$ AE onset date \leq study completion or withdrawal
 - for patients who were followed up off treatment after DB period and then entered the OLE: EoDB $<$ AE onset date $<$ date of first dose of IP in OLE.

Similarly, if an AE has a partial onset date, then unless the partial onset date or the stop date indicates otherwise, it will be summarized in the DB or OLE period based on the imputed onset date (Section 8.6.1.1) compared to the first dose in the respective analysis period.

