8.3.2. Time period and frequency for collecting AE and SAE information

Adverse Events will be collected from time of signature of ICF throughout the treatment period and including the follow-up period.

All SAEs will be recorded and reported to the sponsor or designee within 24 hours, as indicated in [Appendix B](#). The investigator will submit any updated SAE data to the sponsor within 24 hours of it being available.

Investigators are not obligated to actively seek AE or SAE in former study patients. However, if the investigator learns of any SAE, including a death, at any time after a patient's last visit and he/she considers the event to be reasonably related to the Study treatment or study participation, the investigator may notify the sponsor.

The method of recording, evaluating, and assessing causality of AE and SAE and the procedures for completing and transmitting SAE reports are provided in [Appendix B](#).

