8.3.4. Adverse event data collection

The following variables will be collected for each AE:

- AE (verbatim)
- The date when the AE started and stopped
- maximum intensity of the AE
- Whether the AE is serious or not
- Investigator causality rating against the Investigational Product(s) (yes or no)
- Action taken with regard to Investigational Product(s)
- AE caused patient's withdrawal from study (yes or no)
- Outcome

In addition, the following variables will be collected for SAEs:

- Date AE met criteria for serious AE
- Date Investigator became aware of serious AE
- AE is serious due to (specify the SAE criteria per definition in [Appendix B](#))
- Date of hospitalisation
- Date of discharge
- Probable cause of death
- Date of death
- Autopsy performed
- Causality assessment in relation to Study procedure(s)
- Causality assessment to other medication

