9.4.2. Safety analyses

Safety analyses will be performed on the Safety Analysis Set. Treatment-emergent AEs/SAEs will be summarized over the study. In addition, exposure adjusted summaries covering the entire post-treatment (first dose date through to last safety follow-up) will be considered for all patients.

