9.4.2.2. Analyses of safety variables

Safety data will be presented using descriptive statistics unless otherwise specified. In general, the baseline value for statistical analysis is the last non-missing value prior to administration of the first dose of IP. Details will be described in the SAP.

Adverse Events

Adverse events will be coded using the most recent version of the Medical Dictionary for Regulatory Activities (MedDRA) that will have been released for execution at AZ/designee. AEs will be presented for each treatment group by SOC and/or PT covering number and percentage of patients reporting at least one event and number of events where appropriate.

An overview of AEs will present for each treatment group the number and percentage of patients with any AE, AEs with outcome of death, serious AEs, and AEs leading to discontinuation of IP. Separate AE tables will be provided taken into consideration

relationship as assessed by the investigator, intensity, seriousness, death and events leading to discontinuation of IP. An additional table will present number and percentage of patients with most common AEs (frequency of $\geq 3\%$). Key patient information will be presented for patients with AEs with outcome of death, serious AEs, and AEs leading to discontinuation of IP. An AE listing for the safety analysis set will cover details for each individual AE. Full details of AE analyses will be provided in the SAP.

The following events are considered treatment emergent:

- Adverse events with an onset date on or after first dose of IP
- Worsening of pre-existing events on or after first dose of IP

Vital signs

Vital sign parameters will be presented for each treatment group. Summary statistics for continuous variables cover n, Min, median, and Max. For each scheduled post-baseline visit, descriptive statistics for all vital sign parameters will be presented for observed values and change from baseline. Details of vital sign analyses will be provided in the SAP.

Clinical Laboratory Measurements

Laboratory data will be summarized per treatment group by presenting shift tables using normal ranges (baseline to most extreme post-baseline value) and by presenting summary statistics of observed and change from baseline values. Details of laboratory data analyses will be provided in the SAP.

ECG

Summary statistics for the overall evaluation of ECG will be tabulated per treatment group. Details of ECG analyses will be provided in the SAP.

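### SAP 3.8.1 places adverse events by onset date alone, omitting the worsening half of the protocol's treatment-emergent definition and leaving no rule for events that become serious after the switch to open-label treatment

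*SAP*

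**What the plan says.** **Protocol.** AEs are recorded from consent onward (8.3.2: "Adverse Events will be collected from time of signature of ICF throughout the treatment period"), so an AE can begin during run-in. Section 9.4.2 commits to a specific type of summary: "Treatment-emergent AEs/SAEs will be summarized over the study". Section 9.4.2.2 names two kinds of event that qualify: "Adverse events with an onset date on or after first dose of IP", and "Worsening of pre-existing events on or after first dose of IP". Section 8.3.4 lists the data held for each AE: one start date, one stop date and one maximum intensity. For SAEs it adds "Date AE met criteria for serious AE".

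**SAP.** Section 3.8.1 states: "AEs will be separated according to their onset date into the following study periods". The DB period takes AEs with onset from the first DB dose to the end of the DB period. At the switch, any "AE that starts on or after the date of first OLE dose should only be counted in the OLE". The extended follow-up under the early protocol versions is also defined by onset. One other date has a role, for partial onset dates only: "unless the partial onset date or the stop date indicates otherwise". Neither 3.8.1 nor 4.2.10.1 defines treatment-emergent for AEs, mentions worsening, or uses the date on which an event became serious. Section 1.1 says that changes from the protocol will be described; Section 6 lists none.

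**The concern.** Two separate things are at issue.

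The first is a conflict between the documents. The protocol counts a pre-existing event that worsens after the first dose, and the SAP's period rule cannot see it. An AE that began before the first DB dose belongs to none of the periods in 3.8.1. If it later worsens or becomes serious and the change is entered on the same record, it does not reach the DB AE or SAE tables, which carry the only controlled safety comparison in the study.

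The second is a gap. An AE that begins in the DB period and becomes serious after the first open-label dose keeps its DB label. Safety is the primary objective of the OLE (Protocol Table 5, SAP Table 2), and SAP 4.2.10.1 reports OLE SAE summaries as early as the primary database lock. Those summaries can therefore omit an event that became serious on open-label benralizumab.

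**Working it through.** The plan states no figure on this point, so there is none to reproduce. The check applies the SAP 3.8.1 rule to hypothetical timelines.

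Inputs: first DB dose on day 1; first OLE dose on day 393, the scheduled Week 56 day in SAP 3.1.2 (56 × 7 + 1 = 393). The event days are assumed for illustration.

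| Case | Onset used | Period under SAP 3.8.1 |
|---|---|---|
| (a) Run-in AE, onset day −20, worsens day 30, one record | −20 | none |
| (b) As (a), worsening entered as a new AE | 30 | DB |
| (c) DB AE, onset day 380, becomes serious day 420, one record | 380 | DB |
| (d) As (c), serious episode entered as a new AE | 420 | OLE |

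Case (a) is treatment-emergent under Protocol 9.4.2.2 and missing under the SAP. The same holds if the day-30 change is to seriousness. Case (c) is a DB SAE under the SAP although it became serious 420 − 393 = 27 days after the first OLE dose. Cases (b) and (d) show that the onset rule works if the change opens a new record.

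**Do the documents say which applies?** Appendix B 1 of the protocol allows deterioration of an existing condition to be an AE, and SAP 3.8.4 and 3.8.5 have clinically significant aggravated ECG and examination findings reported as AEs. None of these says that worsening of an AE already on record opens a new one. The fields in Protocol 8.3.4 suggest that a single continuing record is possible: a seriousness date separate from the start date is needed only if a record can begin as non-serious.

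**Reach of the protocol definition.** It refers to the first dose of IP, and Protocol Section 6 includes placebo in study treatment. The reference point is therefore the first DB dose in both arms. Case (a) conflicts with the protocol; case (c) falls where the protocol gives no rule.

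**Time at risk.** SAP 4.2.10.1 counts days at risk for the exposure-adjusted incidence rate (EAIR) from the first dose to the start of the AE. In case (a) the start precedes the first dose, so the formula gives no usable time unless the date of the qualifying change is used.

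**Size per event.** Planned allocation is about 250 at 1:1, so 250 / 2 = 125 per arm. One event: 1 / 125 = 0.8 percentage points. Two: 1.6. Five: 4.0.

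**The case against.** The best reply is that worsening may be entered as a new AE, in which case the onset rule places it correctly. That is fair. A reader might infer that worsening is always lost, and the documents do not support this: it depends on recording instructions that they do not contain.

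Three other readings go too far.

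- *That the rule always understates benralizumab's counts.* Run-in events that worsen drop out of both arms. A DB-onset AE in a benralizumab patient that becomes serious in the off-treatment extended follow-up stays in DB, which raises the drug's count.
- *That the event in case (c) necessarily becomes a placebo SAE.* It does for a placebo patient if DB tables use DB treatment. SAP 2.1.3, read literally, assigns anyone with at least one benralizumab dose to the benralizumab group, including placebo patients who enter the OLE.
- *That a share of the OLE SAE count can be put on this.* The documents give no rate of ongoing AEs at Week 56, of later seriousness, or of OLE SAEs. AEs that only worsen cannot be divided by a count of SAEs.

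It is also true that OLE data are descriptive (Protocol 9.1, 9.6) and that patient listings are planned for deaths, SAEs and discontinuations (SAP 4.2.10.1), so boundary cases can be inspected one by one. That limits the harm, but it does not correct the summary counts or reconcile the two documents.

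**Conclusion.** The point holds in a limited form. SAP 3.8.1 omits the second part of the protocol's treatment-emergent definition and Section 6 does not declare it. The direct conflict covers AEs that began before the first DB dose and worsened or became serious afterwards on the same record; these are missing from the DB summaries in either arm. The handling of DB-onset AEs that become serious in the OLE is a gap in both documents, and it can leave such events out of the OLE SAE summary.

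The number of affected events is unknown. Each is worth about 0.8 percentage points of an arm, assuming 125 patients per arm. The direction of any net effect on the DB comparison cannot be stated. The conclusion assumes that at least some worsening stays on the original record, which the data fields allow and no instruction in the documents rules out. The efficacy analyses are not affected.

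**What to change.** In SAP 3.8.1:

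1. Restore the protocol's two-part definition for the DB period. Count a pre-dose AE whose recorded date of meeting serious criteria is on or after the first DB dose, and any worsening entered as a separate AE.
2. For AEs that cross from DB to OLE, place the SAE in the period in which it became serious, using the same date. At minimum, add a supplementary SAE table on that basis.
3. Keep the EAIR time-at-risk rule in 4.2.10.1 consistent with the choice, so that the date that qualifies the event also ends its time at risk.
4. State that DB tables use DB treatment, and limit the classification in 2.1.3 to the analysis period.
5. State how worsening of an AE already on record has been entered. If the sponsor prefers to keep the onset rule unchanged, declare the departure in Section 6.

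The cost is SAP wording, minor reprogramming and one supplementary table; the seriousness date is already collected. The repair has a limit. With one maximum intensity per AE and no date of worsening among the listed variables, worsening without seriousness can be captured only where it was entered as a new record. A new eCRF instruction would not re-date existing entries: enrolment began in November 2019 and the SAP's latest amendment is from June 2024.

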3.8.2 Laboratory variables

Laboratory assessment values and normal ranges will be presented in the International System (SI) unit. Eosinophil data will be presented in both SI and conventional units (cells/ μ L) in summaries.

Changes in haematology and clinical chemistry variables between baseline and each post-baseline assessment will be calculated. There will be no imputation for missing values. For values recorded with a leading greater than or less than ('>', '<') symbol, the reported numeric value will be used for analysis and the value with the symbol will be included in the listings, unless otherwise specified. For example, a value of <0.01 will be analysed as 0.01 and listed as <0.01.

Absolute values will be compared to the relevant reference range and classified as low (below range), normal (within range or on limits) or high (above range). All absolute values falling outside the reference ranges will be flagged. The maximum or minimum value post-baseline will be calculated over the entire DB period and OLE period, respectively, for all patients.

3.8.3 Vital signs

Pre-dose vital signs (pulse, systolic blood pressure, diastolic blood pressure, respiration rate, and body temperature) will be obtained in accordance with schedule provided in the protocol. Changes in vital signs variables between baseline and each post-baseline assessment will be calculated. There will be no imputation for missing values.

Absolute values will be compared to the reference ranges listed in [Table 10](#) and classified as low (below lower limit), normal (within lower limit and upper limit, inclusive) or high (above upper limit). All absolute values falling outside the reference ranges will be flagged.

Table 10 Vital signs reference ranges

Parameter	Standard units	Lower limit	Upper limit
Diastolic blood pressure	mmHg	60	120
Systolic blood pressure	mmHg	100	160
Pulse rate	Beats/min	40	120
Respiratory rate	Breaths/min	8	28
Body temperature	Celsius	36.5	38
Weight	Kg	40	200

CCI
CCI

3.8.4 ECG

ECG measurements will be assessed during the DB period in accordance with the protocol, with the baseline being defined as the last available non-missing measurement prior to first dose of randomised treatment (V3).

The outcome of the overall evaluation is to be recorded as normal/abnormal in the eCRF by the Investigator/authorised delegate, with any abnormalities being recorded as not clinically significant or clinically significant. Any new finding(s) or aggravated existing finding(s), judged as clinically significant by the Investigator, unless unequivocally related to the disease-under-study, will be reported as an AE.

3.8.5 Physical examination

Complete and brief physical examinations will be performed at time points specified in SOA Tables in the CSP. What is included in the assessment will be dependent on whether the examination is complete or brief, as described in Section 8.2.2 of the CSP. Only information on whether the assessment was performed or not is to be recorded. Any new finding(s) or aggravated existing finding(s), judged as clinically significant by the Investigator, unless unequivocally related to the disease-under-study, will be reported as an AE.

4. ANALYSIS METHODS

4.1 General principles

The primary database lock will occur after all randomised patients have been followed up for the 56-week double-blind treatment period. The final database lock will occur after the last patient completes the OLE.

Analyses at the primary DBL will include all data captured during the double-blind treatment period and selected safety endpoints during the OLE period. Unblinding and data analysis will occur after the primary database lock. Efficacy endpoints will be analysed using the PFAS according to their randomised treatment. Efficacy data collected from patients without comorbid asthma will be listed only. Safety endpoints will be analysed using the Safety Analysis Set (or the OLE set if specified) regardless of comorbid asthma status according to their actual treatment received.

In the primary analysis of co-primary endpoints (and key secondary endpoints unless otherwise stated), an ANCOVA model will be used with treatment arm, baseline score (for the respective endpoint), region, CCI [REDACTED] as covariates. Handling strategy of intercurrent events are specified as follows:

- *Nasal polyp surgery*: a nasal polyp surgery is considered as treatment failure. The composite strategy will be applied where the worst possible (WP) score for the respective endpoint will be used for post-surgery assessments.
- *SCS use for CRSwNP*: SCS use for CRSwNP is considered as treatment failure but less severe than surgery. The composite strategy will be applied where the worst observation prior to the SCS use will be carried forward (WOCF) for post-SCS assessments.
- *Treatment discontinuation*: the treatment policy strategy will be applied.

The analysis includes all the data collected during the study including data collected after discontinuation of study treatment except data collected after surgery and/or SCS use for CRSwNP. For participants who discontinue the study without any rescue event (i.e. NP surgery and/or SCS use for CRSwNP), a multiple imputation (MI) approach will be used to impute missing values assuming missing at random (MAR). The estimates of the treatment effects will be based on contrasts from the ANCOVA model.

Details regarding the estimand for primary and key secondary objectives are provided in [Table 11](#), with additional details including supplementary and sensitivity analyses provided in [Appendix 8.2 to 8.5](#) and [Appendix 8.10](#).

Summary data will be presented in tabular format by treatment group. Categorical data will be summarised by the number and percentage of patients in each category. Continuous variables for parametric data will be summarised by descriptive statistics including number of patients in analysis (n), mean, SD, median, and range (minimum (Min), maximum (Max)).

All hypothesis testing will be reported using 2-sided. P-values will be rounded to 4 decimal places. The 95% CI will be reported for efficacy endpoints as appropriate.

The absolute change from baseline is computed as (*visit value* – *baseline value*). Percent change from baseline is computed as (*visit value* – *baseline value*) / *baseline value* × 100%. If either a visit value or the baseline value is missing, the absolute change from baseline value and the percent change from baseline will also be set to missing.

The data analyses will be conducted using the SAS® System (SAS Institute Inc., Cary, NC), version 9.4 or higher. All SAS® programs used to generate analytical results will be developed and validated according to AstraZeneca SAS® programming standards and validation procedures.

Table 11 Estimand for primary and key secondary objectives and safety objectives

Statistical Category & Section	Estimand ¹			
	Treatment Condition ¹	Endpoint (Population)	Intercurrent Event Strategy ¹	Population Level Summary ¹ (Analysis)
Primary Objective: To evaluate the effect of benralizumab on nasal polyp burden and patient-reported nasal blockage				
Co- Primary/MCP Section 4.2.5.1	Treatment with benralizumab versus placebo, regardless of compliance, where rescue indicates treatment failure.	
 CFB in endoscopic total NPS (severe CRSwNP patients with asthma) CFB in bi-weekly mean NBS (severe CRSwNP patients with asthma) 	
 Treatment discontinuation –treatment policy Surgery for CRSwNP– composite (Worst Possible) SCS use for CRSwNP – composite (WOCF) 	Mean difference between interventions at Week 56 ² (LSMD from CFB ANCOVA following hybrid WP/WOCF and MI).
Key Secondary Objective: To evaluate the effect of benralizumab on sense of smell				
Secondary/MCP Section 4.2.6.1	Treatment with benralizumab versus placebo, regardless of compliance, where rescue indicates treatment failure.	
 CFB in bi-weekly mean DSS (severe CRSwNP patients with asthma) 	
 Treatment discontinuation –treatment policy Surgery for CRSwNP – composite (Worst Possible) SCS use for CRSwNP – composite (WOCF) 	Mean difference between interventions at Week 56 ² (LSMD from CFB ANCOVA following hybrid WP/WOCF and MI).
Key Secondary Objective: To evaluate the effect of benralizumab on sinus opacification				
Secondary/MCP Section 4.2.6.2	Treatment with benralizumab versus placebo, regardless of compliance, where rescue indicates treatment failure.	
 CFB in mean LMS (severe CRSwNP patients with asthma) 	
 Treatment discontinuation –treatment policy Surgery for CRSwNP – composite (Worst Possible) SCS use for CRSwNP – treatment policy 	Mean difference between interventions at EoDB/IPD (LSMD from CFB ANCOVA following WP imputation).
Key Secondary Objective: To evaluate the effect of benralizumab on disease specific health-related quality of life				
Secondary/MCP Section 4.2.6.3	Treatment with benralizumab versus placebo, regardless of compliance, where rescue indicates treatment failure.	CFB in SNOT-22 score (severe CRSwNP patients with asthma)	
 Treatment discontinuation –treatment policy Surgery for CRSwNP – composite (Worst Possible) SCS use for CRSwNP – composite (WOCF) 	Mean difference between interventions at Week 56 ² (LSMD from CFB ANCOVA following hybrid WP/WOCF and MI).
Safety Objective: To evaluate the safety and tolerability of benralizumab				

Safety Section 4.2.10.1
	
Treatment with benralizumab, regardless of compliance, versus placebo, regardless of compliance.
	
 • Presence of AEs and SAE (all severe CRSwNP patients regardless of co-morbid asthma status) 	
Treatment discontinuation –treatment policy
	
Categorical descriptive

--	---	--	--	--------------------------------

MCP = Multiple comparisons procedure; CRSwNP = Chronic rhinosinusitis with nasal polyps; SCS = Systemic Corticosteroids; NPS = Nasal Polyps Score; NBS = Nasal Blockage Score; DSS = Difficulty with Sense of Smell; SNOT-22 = SinoNasal Outcome Test, 22 item; LMS = Lund-Mackay score; WP = Worst Possible; WOCF = Worst Observation Carried Forward; MI = Multiple Imputation; LSMD = Least Squares Mean Difference; CFB = Change from baseline; ANCOVA = Analysis of Covariance; EoDB = End of treatment in double-blind period; IPD = Investigational product discontinuation; AE = Adverse event; DB = Double-blind.

[1] All estimand attributes explicitly identified for primary and key secondary endpoints only.

[2] Week 56 is the multiplicity protected timepoint for co-primary and key secondary endpoints.

